### **15.3.2. Treatment Groups**

There will be a single treatment group to be analyzed following this amendment, and that is the subjects who remained in the OLE study under Protocol Amendment 3.

### **15.3.3. Statistical Methods**

#### **15.3.3.1. Interim Analyses**

Not applicable.

#### **15.3.3.2. Adjustment for Multiple Comparisons/Multiplicity**

No adjustment for multiplicity will be performed. All analyses will be descriptive.

#### **15.3.3.3. Missing Data Handling**

For all efficacy endpoints based on patient-reported outcome/clinical outcome assessment instruments, the scoring algorithms (including the standard or published data imputation or pro-rating methods contained in the scoring algorithms) will be implemented.

No data imputation are planned for missing efficacy data. If any imputations are decided upon later, the details will be provided in the statistical analysis plan.

In general, missing safety data will not be imputed. However, attributes such as missing dates for AEs and concomitant medications will be imputed using similar methods as described for ATB200-03 in order to ensure consistency. Details will be provided in the statistical analysis plan.

#### **15.3.3.4. Windowing Conventions**

By-visit assessments for safety and efficacy will be summarized based on visit windows.

#### **15.3.3.5. Statistical Tests**

No formal hypotheses are planned to be tested. Unless otherwise specified, only descriptive statistics will be presented. Any inferential analyses will be presented for summary purposes. Where appropriate, 2-sided 95% confidence intervals will also be provided for summary purposes.

#### **15.3.3.6. Common Calculations**

In general, continuous variables will be summarized using descriptive statistics (the number of subjects with available data, mean, standard deviation, median, minimum, and maximum). Categorical variables will be summarized using counts and percentages.

### **15.3.4. Analyses**

All analyses under this amendment will be based only on the stand-alone additional data collected following the database lock (DBL) for the final CSR, and there will be no integration with any data that existed prior to the DBL.

In general, continuous data will be summarized using descriptive statistics, and categorical data will be summarized using counts and percentages. Specific analysis details and display format will be described in the statistical analysis plan.

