## **8.4. Definition of the End of Study**

End of study is defined as the date of the last subject's last visit. The final analysis will be performed for the final CSR based on a data cutoff date of 31 December 2024. Any data collected after this date will be provided as an addendum to the final CSR when all subjects have completed the study or have been withdrawn from the study. Upon approval of this amendment, subjects who remain in the study will follow the Schedule of Assessments in [Appendix 1](#) ([Table 10](#)).

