## **15. DATA ANALYSIS AND STATISTICAL CONSIDERATIONS**

The final analysis of the whole data set detailed in this section will be performed for the final CSR based on a data cutoff date of 31 December 2024. Any data collected after this date will be provided as an addendum to the final CSR when all subjects have completed the study or have been withdrawn from the study.

For subjects continuing in the study after approval of this amendment, please refer to [Appendix 1](#) for details on the data analysis and statistical considerations.

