### 8. INVESTIGATIONAL PLAN

#### 8.1. Study Design

This is a multicenter, international, open-label extension study of cipaglucosidase alfa/miglustat in adult subjects with LOPD who completed Study ATB200-03. No additional subjects will be enrolled after data cutoff date of 31 December 2024.

Upon approval of this amendment, any subjects continuing in the study will follow the updated Schedule of Assessments in [Table 10](#).

Upon approval of this amendment, study visits that include minimal efficacy, safety, and other assessments will be scheduled approximately every 52 weeks. These visits may occur over 2 days, provided all study assessments and procedures are performed before administration of study drug. The relevant IRBs, ECs, and REBs should be notified of any deviations from the protocol.

Efficacy assessments (ie, functional assessments) include evaluation of ambulatory function (6MWT) and pulmonary function tests (FVC). Safety assessments include monitoring of AEs, including IARs, vital signs, physical examinations including weight. Concomitant medications and nondrug therapies will also be recorded.

The study will continue until one of the conditions outlined in Section [8.2](#) in the main body of the protocol is met.

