##### **15.3.4.1.1. Analyses of Ambulatory Function and Pulmonary Function**

Efficacy variables (6MWD [m]), percent predicted 6MWD, and percent predicted sitting FVC) will be summarized over time for the assessment visits that occurred post-DBL of the final CSR, based on the OLE-RS population. Where a change from baseline summary is required, the baseline result will be based on the last assessment prior to the DBL of the final CSR. A 95% confidence interval for the mean change from baseline will be provided where applicable. For the analysis of percent predicted 6MWD, the predicted value will be calculated using the reference equations from Enright and Sherill ([Enright and Sherill 1998](#)).

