## 1. INTRODUCTION

This statistical analysis plan (SAP) describes the planned data analyses and the outputs to be included in the final clinical study report (CSR) for the standalone open-label extension (OLE) Study ATB200-07. The SAP is based on Amendment 3 of the Protocol for Study ATB200-07 dated 10 December 2024.

This final SAP describes the analyses that will be performed for the final CSR for the standalone Study ATB200-07 based on a data cutoff date of 31 December 2024. All data collected through the cutoff date will be reported as summary tables and/or listings.

This SAP has been developed in accordance with Good Clinical Practice (GCP), International Council on Harmonisation (ICH) guideline E9 (Statistical Principles for Clinical Trials), and Amicus standard operating procedure (SOP) ATCRA-SOP-AT-008.

The analyses and statistical methods specified in the final SAP supersede those described in the study protocol.

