## 4.4. Data Handling

### 4.4.1. Study Day

For the purposes of analysis, the date of first dose of study drug (First Dose Date) in ATB200-07 is designated as Day 1 and it will serve as the reference start date. The following relative days are considered:

- Total duration of treatment (ie, exposure) will be calculated as: (last dose date prior to data cutoff – first dose date) + 1.
- If the date of interest occurs on or after the first dose date, then study day will be calculated as: (date of interest – first dose date) + 1.
- If the date of interest occurs prior to the first dose date, then study day will be calculated as: (date of interest – first dose date).

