### **5.3.1. Study Compliance**

Compliance will be provided separately for cipaglucosidase alfa and miglustat. For each subject taking cipaglucosidase alfa, compliance will be calculated based on the number of infusions as well as the actual infusion dose administered.

Compliance based on infusion dose is calculated as:

100\*(total infusion dose administered [mg] / total infusion dose planned or intended [mg]).

Compliance based on number of infusions is calculated as:

100\*(number of infusions administered / number of infusions planned or intended),

where the number of infusions planned is obtained as: (subject's last date in ATB200-07 as of the data cut-off date – date of first infusion + 14) / 14.

Compliance for each subject taking miglustat will be calculated as:

100\*(total dose administered [mg] / planned dose [mg]).

Dose compliance rate will be classified as under-compliance: < 80%, within compliance: (80%, 120%), and over-compliance: > 120%.

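### Appendix 1 starts the addendum analyses at database lock, while the protocol body starts the addendum at the 31 December 2024 cutoff, so data between the two dates have no planned summary

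*Protocol*

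**What the plan says.** The protocol body starts the addendum at the cutoff. After naming 31 December 2024 as the cutoff for the final CSR, Section 8.4 states: "Any data collected after this date will be provided as an addendum to the final CSR". Sections 15 and 16.6 repeat the commitment.

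The SAP closes the final CSR at the same date. Its Introduction says "All data collected through the cutoff date will be reported as summary tables and/or listings". Treatment duration in SAP Section 4.4.1 runs to the "last dose date prior to data cutoff", and the planned number of infusions in SAP Section 5.3.1 runs to the subject's "last date in ATB200-07 as of the data cut-off date".

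Appendix 1, Section 15.3.4, starts the addendum analyses elsewhere: "All analyses under this amendment will be based only on the stand-alone additional data collected following the database lock (DBL) for the final CSR". The same sentence excludes integration with data that existed before the lock. Sections 15.3.4.1.1 and 15.3.4.2 of the appendix apply the rule to efficacy visits and visit-based safety variables by selecting visits that took place after the lock. On change from baseline, Section 15.3.4.1.1 says "the baseline result will be based on the last assessment prior to the DBL of the final CSR", and Section 15.3.4.2 has the matching rule for safety.

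Appendix 1, Section 15.3.1, names one population for all addendum analyses, OLE-RS: subjects who stayed in the study and went on receiving treatment under Amendment 3.

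**The concern.** The two reports are meant to cover the whole study between them. If the first ends at the cutoff and the second begins at a later lock, the interval between belongs to neither. Subjects are dosed every 2 weeks throughout it, so the interval holds exposure and possibly adverse events, serious adverse events and infusion-associated reactions. Because long-term safety is the primary objective, a reader who adds the two reports together would undercount both events and time on treatment, by an amount the reports would not show.

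There are two further effects. The addendum baseline for 6MWD, FVC, laboratory, ECG or vital-sign data could be a value from the gap, that is, one that no by-visit table presents. Separately, OLE-RS leaves out anyone who stopped treatment or died after the cutoff without being dosed under Amendment 3, so that person's events after the cutoff would also go unsummarised.

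**Working it through.** The plan states no figure to reproduce. The check compares where each report starts and stops.

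| Report | Source | Starts | Ends |
|---|---|---|---|
| Final CSR | SAP 1, 4.4.1, 5.3.1 | first dose in ATB200-07 | 31 December 2024 |
| Addendum, protocol body | Protocol 8.4, 15, 16.6 | after 31 December 2024 | last subject out |
| Addendum, appendix | Appendix 1, 15.3.4 | after database lock | last subject out |

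**1. Are lock and cutoff the same date?** Nothing says so. Appendix 1 uses the cutoff by name in its own Section 8.1, "No additional subjects will be enrolled after data cutoff date of 31 December 2024", and changes to the lock only in Section 15.3.4 and its subsections. Protocol Section 14 treats database lock as an operational event, after which sites receive their data files. A lock on data through 31 December 2024 cannot come before that date, so the gap is zero only if both fall on the same day.

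**2. Could data collected after the lock mean data entered after the lock?** Not for visit data: Appendix 1, Sections 15.3.4.1.1 and 15.3.4.2, select by when the visit took place.

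**3. What has a route into a report?** A gap value of 6MWD, FVC, a laboratory test, ECG or vital sign can enter as the addendum baseline, but not as a follow-up result. Adverse events, serious adverse events, infusion-associated reactions and exposure have no route, because Section 15.3.4 covers all analyses under the amendment.

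**4. How large could the gap be?** Its length is the lock date minus 31 December 2024, and the lock date is not given. The values of *w* below and the 30 subjects are assumptions. From the documents come dosing every 2 weeks (Protocol 10) and assessment visits every 26 weeks (Table 4) or every 52 weeks (Table 10). Visit dates are taken as evenly spread.

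- Infusions per subject = *w*/2
- Person-years per subject = 7*w*/365.25
- Share of subjects with an assessment visit in the gap = *w*/26 (at most 1) or *w*/52

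| Assumed gap *w* | Infusions per subject | Person-years per subject | Person-years per 30 subjects | Share, 26-week visits | Share, 52-week visits |
|---|---|---|---|---|---|
| 4 weeks | 2 | 28/365.25 = 0.077 | 2.3 | 15% | 8% |
| 13 weeks | 6.5 | 91/365.25 = 0.249 | 7.5 | 50% | 25% |
| 26 weeks | 13 | 182/365.25 = 0.498 | 14.9 | 100% | 50% |

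The 26-week column applies only while the old schedule is in force. Subjects move to 52-week visits once Amendment 3 is approved.

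**5. Does moving the start date capture everyone?** Not quite. Protocol Section 13.1.2 and SAP Section 7.2 follow adverse events to 30 days after the last dose. A last dose on 2 December 2024 plus 30 days is 1 January 2025, so follow-up after any last dose on or after 2 December passes the cutoff. If such a subject was never dosed under Amendment 3, the January events fall after the final CSR data and outside OLE-RS. The number is unknown and may be zero, since approval dates are not given.

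**The case against.** The best reply is that the intent is plain. The protocol body says three times that data after the cutoff go into the addendum, and Appendix 1 calls its data additional, so the lock may be loose shorthand for the final CSR dataset. That is plausible, but the literal text of Section 15.3.4 is against it, and the appendix uses the cutoff by name elsewhere.

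Second, Appendix 1 defers details to a statistical analysis plan, which could settle the start date. The supplied SAP covers only the final CSR. A later plan that began at the cutoff would have to override Section 15.3.4, not merely add detail to it. This supports stating the date now; it does not remove the conflict.

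Third, Sections 8.4, 15 and 16.6 promise that the data will be provided, which listings might satisfy. That would still leave no summary of the gap.

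Fourth, the lock restriction in Appendix 1, Section 15.3.4.2, is attached only to visit-based variables. For adverse events and exposure the point therefore rests on the general rule in Section 15.3.4 alone. Likewise, the exposure formula in SAP Section 5.3 carries no cutoff of its own, though the SAP Introduction supplies one. Both observations are correct, and neither changes the result.

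Fifth, no integrated or exposure-adjusted analysis across the two reports is planned, so no planned table becomes wrong. This stands, and it limits the harm to incomplete coverage. The OLE-RS point is separate from the date conflict and may affect nobody.

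**Conclusion.** The concern holds. The protocol gives two start points for the addendum, and following Appendix 1 leaves adverse events, serious adverse events, infusion-associated reactions and exposure between the cutoff and the lock without a planned summary. That conflicts with Sections 8.4, 15 and 16.6 and should be fixed.

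The contradiction is certain from the text; its size is not. It depends on a lock date and a number of continuing subjects that the documents do not give, so the tabulated figures are illustrations only. The harm is bounded: the final CSR is complete through its cutoff, reporting of serious adverse events to the sponsor continues under Protocol Section 13.3, and the study is descriptive. What is lost is full coverage of time on treatment across the two reports.

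**What to change.** In Appendix 1, Sections 15.3.4, 15.3.4.1.1 and 15.3.4.2, replace the database lock of the final CSR with the 31 December 2024 data cutoff. Addendum data then start on 1 January 2025, and baseline is the last assessment on or before the cutoff. The uncovered interval becomes zero days whatever the lock date, and the addendum baseline comes from data the final CSR reports.

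For the addendum safety tables, include every subject with treatment or 30-day adverse-event follow-up after the cutoff, whether or not dosed under Amendment 3. Keep OLE-RS as defined for efficacy.

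The cost is a wording change through the formal amendment procedure (Protocol Section 16.3.4) and matching text in the addendum analysis plan, where the start date can be stated first. No new data and no new visits are required.

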## **6.6. Summary of Known and Potential Risks and Benefits**

Based on efficacy and safety information in the Investigator's Brochure, the benefit-risk balance of cipaglucosidase alfa/miglustat remains positive overall. Cipaglucosidase alfa/miglustat has demonstrated clinically significant benefits in the treatment of Pompe disease, and no important risks have been identified that would preclude the use of cipaglucosidase alfa/miglustat. Mild to moderate IARs have been identified in ongoing clinical studies and are manageable with reduction or temporary stopping of infusion and premedication with corticosteroids, antihistamines, and acetaminophen. No life-threatening or fatal IARs have been observed in clinical studies to date. As with any investigational new drug (IND) or research study procedure, there are risks that are not known that may be serious and may even cause death. The most up to date information regarding efficacy, safety, and benefit-risk assessment for cipaglucosidase alfa/miglustat can be found in the current Investigator's Brochure.

Cipaglucosidase alfa/miglustat has proven overall to be generally safe and relatively well tolerated. Alternative treatments provide initial benefit to patients with Pompe disease. The magnitude and duration of therapeutic response with continuing therapy varies among individual subjects and, at best, may offer improvement in measures of muscle function, strength, and respiratory function for a finite duration, ie, 2 to 3 years in most subjects, followed by a slow decline in these parameters. These alternative treatments may themselves be associated with significant risks. A monthly review for safety signals is part of routine pharmacovigilance.

The strength of the current benefit-risk analysis is based on the safety pool of data from a variety of sources (clinical study, literature, and independent registries) and in various geographies (eg, EU, Australia, and US) while the mean duration of treatment is approaching 36 months.

Weakness of the data is primarily based on the small number of subjects in the clinical study described. There are no specific studies that target specific subpopulations of patients such as elderly, or subpopulations. Uncertainties exist over the long-term safety profile.

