### 7. OBJECTIVE

The objective of this amendment is to continue collecting long-term safety and efficacy data on LOPD subjects treated with cipaglucosidase alfa/miglustat while decreasing some of the burden on those subjects taking part, and continuing to provide treatment where regulatory approval has not yet been granted or the product is not yet commercially available.

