#### **15.3.4.2. Safety Analyses**

Safety data will be summarized on the OLE-RS population. Visit-based safety variables will be summarized over time for the assessment visits that occurred post-DBL of the final CSR. Where change from baseline or percent change from baseline summaries are required, the baseline results will be based on the last assessment made prior to the DBL of the final CSR.

Safety data will be summarized using descriptive statistics for continuous data and using counts and percentages for categorical data, as described in Section [15.3.3.6](#).

Exposure to study medication will be calculated in weeks and analyzed as continuous variables using descriptive statistics. In addition, the duration of exposure will be categorized and a frequency distribution of the categories (each summarized by count and percentage) will be presented.

An overall summary of incidence of AEs (which includes the total number of TEAEs, total number of serious TEAEs as well as the total number of subjects) will be presented. The number and percentage of subjects who experienced nonserious TEAEs as well as serious TEAEs will be summarized by preferred term within system organ class. The summary of nonserious and serious TEAEs will also be presented by intensity (mild, moderate, severe), as well as by relationship to study medication. In addition, the number of AEs (as opposed to the number and percentage of subjects) will be presented.

Serious adverse events, including deaths, will be summarized and listed. Separate listings of death, SAEs (treatment-emergent and nontreatment-emergent), and discontinuations due to AEs will be provided.

Summaries and listings will also be provided for deaths, SAEs, and AEs leading to discontinuation and infusion-associated reactions. Adverse events will be coded using Medical Dictionary for Regulatory Activities version 18 or higher.

Clinical laboratory results, ECG parameters, and vital signs will be summarized using descriptive statistics (number, mean, median, standard deviation, minimum, and maximum) by treatment group and visit for actual values and changes from baseline. The proportion of subjects with abnormalities will be provided for clinical laboratory results, ECGs, and vital signs. Shift tables will also be provided for clinical laboratory results.

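### The Amendment 3 addendum is limited to post-lock data with a reset baseline, so it gives no cumulative change, exposure or adverse-event incidence for the continuing subjects

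*Protocol*

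**What the plan says.** Appendix 1, Section 7 states the aim: "The objective of this amendment is to continue collecting long-term safety and efficacy data on LOPD subjects treated with cipaglucosidase alfa/miglustat", with less burden on subjects and continued access to treatment. Appendix 1, Section 15.1.1 adds that the long-term safety profile will be characterized.

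The analysis rule is in Appendix 1, Section 15.3.4: "All analyses under this amendment will be based only on the stand-alone additional data collected following the database lock (DBL) for the final CSR". The same sentence goes on to rule out any pooling with what came before: "there will be no integration with any data that existed prior to the DBL". For efficacy, Section 15.3.4.1.1 says that, where change is summarized, "the baseline result will be based on the last assessment prior to the DBL of the final CSR". For safety, Section 15.3.4.2 says "the baseline results will be based on the last assessment made prior to the DBL of the final CSR". Section 15.3.2 states: "There will be a single treatment group to be analyzed following this amendment". All of this applies to the OLE-RS population (Section 15.3.1), meaning subjects who stayed in the study and continued treatment under the amendment.

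The final CSR works differently. SAP Section 4.4.2 takes the last value on or before the first ATB200-07 dose as baseline. SAP Section 4.2 splits subjects by original ATB200-03 treatment, and SAP Sections 4.1.3 and 6.1 report efficacy in the FAS. The SAP (Section 1) covers only the final CSR, to the 31 December 2024 cutoff.

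**The concern.** Durability is a question about time since a treatment milestone. Protocol Section 6.6 describes alternative treatments as helping "for a finite duration, ie, 2 to 3 years in most subjects, followed by a slow decline in these parameters", and says that uncertainty remains about the long-term safety of the study product. The subjects who continue under Amendment 3 will have the longest follow-up in the study.

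Resetting zero at an administrative date removes the time axis for exactly these subjects. Subjects with different lengths of earlier treatment all start again at zero, in one group. A slow change that began before the lock would appear in the addendum's change tables only as its post-lock part. Adverse events and exposure would be counted from the lock only. No supplied document plans a table that links the CSR and addendum segments of the same subject.

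**Working it through.** The plan states no power, sample-size or effect figure on this point, so there is none to reproduce. The check compares sections, followed by two illustrations.

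**1. What can be derived from the addendum as written**

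| Quantity for OLE-RS | Needs | Available under 15.3.4? |
|---|---|---|
| Actual 6MWD, % predicted 6MWD, sitting % predicted FVC at post-lock visits | post-lock data | yes |
| Change from last pre-lock value | one pre-lock value | yes, by 15.3.4.1.1; barred by a literal reading of 15.3.4 |
| Change from ATB200-07 baseline | pre-lock data | no |
| Cumulative ATB200-07 exposure | pre-lock data | no |
| Cumulative adverse-event incidence | pre-lock data | no |

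**2. Whether CSR and addendum means can be added**

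For the OLE-RS subjects,

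mean(post-lock value − ATB200-07 baseline) = mean(reference − ATB200-07 baseline) + mean(post-lock value − reference).

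Both terms on the right must come from the same subjects. The addendum gives the second term in OLE-RS. The CSR gives change from the ATB200-07 baseline in the FAS, by visit window. Who remains in OLE-RS depends on local approval, commercial availability and withdrawal (Protocol Sections 6.7 and 8.2). The two published means therefore do not sum to the cumulative change.

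**3. Cutoff against lock**

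Protocol Sections 8.4, 15 and 16.6 send all data collected after 31 December 2024 to the addendum. Appendix 1, Section 15.3.4 admits only data collected after the lock. Data between the two dates are analysed in neither report, except that one assessment may serve as the addendum baseline. In that case the change from the last pre-cutoff value to that baseline is also lost.

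The documents give no lock date. Assume a lag of 60 to 180 days and evenly spread visits:

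- Two-weekly infusions in the gap: 60/14 = 4.3 to 180/14 = 12.9 per subject.
- Share of subjects with a 26-weekly visit in the gap: 60/182 = 33% to 180/182 = 99%.
- Share on the 52-weekly schedule: 60/364 = 16% to 180/364 = 49%.

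**4. Exposure, as an illustration**

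Assumptions: the lock lag above; follow-up to 31 December 2027 (a date that stands in main-body Table 4, while Table 10 has no calendar end); 48 to 60 months of ATB200-07 exposure at cutoff; 30.4 days per month as in SAP Section 5.3.

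- Cutoff to horizon: 1095 days, or 1095/30.4 = 36.0 months.
- Post-lock exposure: (1095 − 60)/30.4 = 34.0 months to (1095 − 180)/30.4 = 30.1 months.
- Cumulative exposure: 48 + 36.0 = 84.0 months to 60 + 36.0 = 96.0 months.
- Share shown by the addendum: at most 34.0/84.0 = 41%, at least 30.1/96.0 = 31%.

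**5. 6MWD, as an illustration by assumption only**

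With a constant slope *s*, 5 years before the reset and 1 year after, total change is 6*s* and the addendum's change is 1*s*. For *s* = −5 m/year this is −30 m against −5 m. For −2 and −10 m/year it is −12 against −2 m and −60 against −10 m. The ratio of one sixth follows from the assumed 5 and 1 years and says nothing about this trial's data.

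**The case against.** A reader might infer that the amendment cannot deliver long-term data at all, or that the longest-treated subjects add nothing to the secondary objectives. The documents do not support either reading.

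- The restriction is on analysis. Collection continues, and the linked subject-level data remain.
- Actual values are still reported: the efficacy variables "will be summarized over time for the assessment visits that occurred post-DBL of the final CSR, based on the OLE-RS population". A reduced 6MWD stays visible in absolute terms, and visits recur every 52 weeks, so there may be more than one.
- Protocol Section 7 ties the secondary objectives to the final CSR. That report gives change from the ATB200-07 baseline in windows running past Day 1548 (SAP Table 3), exposure categories to more than 60 months (SAP Section 5.3), and results by original treatment group. The 2-to-3-year course in Section 6.6 concerns alternative treatments, and the CSR already spans that length of follow-up.
- Using one pre-lock value as a reference can be read as a specific exception to the general rule, so that conflict is mainly one of wording.
- OLE-RS is a selected remainder. For subjects who continued cipaglucosidase alfa/miglustat, the ATB200-07 baseline already follows treatment. The study is uncontrolled and descriptive.
- Appendix 1 defers details to a SAP, and the supplied one covers only the CSR, so the absence of a linking table from it is weak evidence.

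All of this stands and limits the harm. It does not remove the point. The no-integration rule is in the protocol itself, the CSR's efficacy means come from the FAS and not OLE-RS, and selection is a reason to link values within the same subjects and to state the limitation.

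**Conclusion.** The point holds in a limited form. As written, the addendum gives no change from the ATB200-07 baseline, no cumulative exposure and no cumulative adverse-event incidence for the OLE-RS subjects. That fits poorly with the long-term aim in Appendix 1, Sections 7 and 15.1.1, and the CSR does not fill the gap. This conclusion rests on the text alone.

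Separately, Section 15.3.4 of Appendix 1 needs rewriting in any case. Taken literally, it excludes the baseline that Sections 15.3.4.1.1 and 15.3.4.2 require, and it conflicts with Sections 8.4, 15 and 16.6 over data between cutoff and lock.

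The sizes are illustrative. The 31% to 41% share of exposure depends on the assumed lock lag, horizon and prior exposure. It describes the addendum alone, not the CSR and addendum together. The 6MWD example is true by construction and should not be read as an estimate of hidden decline. The change is worth making because it serves the long-term question with data already held. No hypothesis test or trial conclusion is invalidated by its absence.

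**What to change.** In Appendix 1, or in the addendum SAP with a matching protocol correction:

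1. Replace the no-integration sentence in Section 15.3.4. Start the addendum period on the day after the 31 December 2024 cutoff.
2. In Sections 15.3.4.1.1 and 15.3.4.2, take the reference value as the last assessment on or before the cutoff, so that the CSR and addendum periods meet.
3. Keep the planned post-CSR summaries. Beside them, for OLE-RS, add by-visit change from the ATB200-07 baseline in 6MWD, % predicted 6MWD and sitting % predicted FVC, timed from the first ATB200-07 dose. Add cumulative ATB200-07 exposure and adverse-event incidence. Show these overall and, where numbers allow, by original treatment group.
4. State that OLE-RS is a selected remainder, that the ATB200-07 baseline is not a pre-treatment value for subjects who continued cipaglucosidase alfa/miglustat, and that the summaries are descriptive.

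The cost is wording, a merge of data already held and a small amount of extra programming. No visits, assessments or subjects are added, so the reduced-burden aim is untouched.
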